#### **7.1.3.2 Delay of Study Vaccination**

If any of these events occur at the time scheduled for vaccination, the subject may be vaccinated at a later date, within the window specified in the SOA, or the subject may be withdrawn from dosing at the discretion of the participating site PI or appropriate sub-investigator:

- Acute moderate or severe infection with or without fever at the time of vaccination.
- Fever, defined as oral temperature  $\geq 38.0^{\circ}\text{C}$  ( $100.4^{\circ}\text{F}$ ) at the time of vaccination.

Subjects with a minor illness without fever, as assessed by the participating site PI or appropriate sub-investigator, can be administered vaccines. Subjects with an oral temperature of  $38.0^{\circ}\text{C}$  ( $100.4^{\circ}\text{F}$ ) or higher will be re-contacted within the window specified in the SOA and re-evaluated for eligibility.

#### **7.1.4 Follow-up for Subjects that Discontinued Study Intervention**

Discontinuation of study intervention does not require discontinuation from the study, and the remaining study procedures should be completed as indicated by the SOA. If a clinically significant finding is identified, including, but not limited to, changes from baseline, after enrollment, the participating site PI or qualified designee will determine if any change in subject management is needed. Any new clinically relevant finding will be reported as an AE.

The data to be collected at the time of study intervention discontinuation should include the following:

- Clinical safety laboratory evaluations.
- Complete physical examination.

- Vital signs (BP, heart rate [HR], oral temperature).
- Immunogenicity evaluations.

## 7.2 Subject Withdrawal from the Study and Replacement

Subjects are free to withdraw from participation in the study at any time upon request, without any consequence.

A study subject will be discontinued from participation in the study if any of the following reasons occur prior to initial dosing:

- Request by the subject to terminate participation.
- Vaccine is not administered.

A subject may be removed from the study for the following reasons post initial dosing; however, whenever possible the subject should be followed for safety and immunogenicity evaluations per protocol:

- Subject becomes pregnant before receiving the second dose of vaccine.
- Study non-compliance to protocol requirements that in the opinion of the participating site PI or appropriate sub-investigator poses an increased risk (e.g., missing safety labs) or compromises the validity of the data.
- Lost to follow-up.
- If the subject met an exclusion criterion for participation in the study (either newly developed or not previously recognized) that precludes further study participation.
- Request of primary care provider; the IRB, FDA, or NIAID.
- Medical disease or condition, or new clinical finding(s) for which continued participation, in the opinion of the participating site PI or appropriate sub-investigator might compromise the safety of the subject, interfere with the subject's successful completion of this study, or interfere with the evaluation of responses.
- If any AE, clinical laboratory abnormality or situation occurs such that continued participation in the study would not be in the best interest of the subject.
- The occurrence of an SAE.

If the subject agrees, every attempt will be made to follow all AEs through resolution or stabilization.

Subjects who withdraw, or are withdrawn from this study, or are lost to follow-up after signing the informed consent form (ICF) and administration of the study product will not be replaced.

Subjects who withdraw, or are withdrawn from this study, or are lost to follow-up after signing the ICF but before administration of the study product may be replaced.

The reason for subject discontinuation or withdrawal from the study will be recorded on the appropriate DCF.

### **7.3 Lost to Follow-Up**

A subject will be considered lost to follow-up if he or she fails to appear for a follow-up assessment. Extensive effort (i.e., generally three documented contact attempts via telephone calls, e-mail, etc., made on separate occasions) will be made to locate or recall the subject, or at least to determine the subject's health status. These efforts will be documented in the subject's study file.

## **8. STUDY ASSESSMENTS AND PROCEDURES**

### **8.1 Screening and Immunogenicity Assessments**

#### **8.1.1 Screening Procedures**

There is a small amount of risk to subjects who report that they are in good health but have an unknown health problem at the time of screening. Screening assessments can occur up to 42 days before the subject's first vaccination (Day 1) and may occur in one or two visits. At the first visit, and prior to any other study-related activities, the participating site PI or appropriate sub-investigator will provide the subject with detailed study information and will obtain written informed consent.

Some or all of the following assessments are performed during the screening visit to determine eligibility requirements as specified in the inclusion and exclusion criteria:

- Obtain medical history.
- Review pre-study medications and therapies up to 30 days prior to the start of screening and record on the appropriate DCF.
- Review of adult vaccinations, including any other SARS-CoV-2 or other experimental coronavirus vaccines.
- Measure vital signs (HR, BP, and oral temperature) and height and weight for determination of BMI.
- Perform full physical examination which will include assessments of the following organs and organ systems: skin, head, ears, eyes, nose, and throat (HEENT), neck, lungs, heart, liver, spleen, abdomen, extremities, lymph nodes (axillary and cervical), and nervous system.
- Review of birth control history with female subjects.
- Counsel subjects to use adequate birth control methods required during the trial to avoid pregnancy.
- Obtain blood and urine for clinical screening laboratory evaluations:
  - Hematology
    - WBCs
    - Hgb
    - PLTs
  - Chemistry (fasting or non-fasting)

- ALT
- AST
- ALP
- T. Bili
- Lipase
- Cr
- PT
- PTT
- Serology
  - Hepatitis B surface antigen
  - Hepatitis C virus antibody
  - HIV types 1 and 2 antigen/antibody
- Serum pregnancy test (in women of childbearing potential)
- Urine drug screen
- Review inclusion and exclusion criteria.

Clinical screening laboratory evaluations will be performed locally by the site laboratory. The volume of venous blood to be collected for these evaluations is presented in Table 8.

The overall eligibility of the subject to participate in the study will be assessed once all screening values are available. The screening process can be suspended prior to complete assessment at any time if exclusions are identified by the study team.

Study subjects who qualify for inclusion will be contacted and scheduled for enrollment and first vaccination within the window for enrollment.

If a physiologic parameter, e.g., vital signs or clinical laboratory value, is outside of the protocol-specified range, then the measurement may be repeated once if, in the judgment of the participating site PI or appropriate sub-investigator, the abnormality is the result of an acute, short-term, rapidly reversible condition (e.g., stress, anxiety or “white coat syndrome”) or other source of error. A physiologic parameter may also be repeated if there is a technical problem with the measurement caused by malfunctioning, or an inappropriate measuring device (i.e., inappropriate-sized BP cuff).

A subject may be re-screened if there is a transient disease status (e.g., subject complained of a “cold or fever” and met a temporary delaying enrollment criterion of acute illness or fever), or if a protocol eligibility criterion that is not met at the initial time of screening, will be met by rescreening at a later date (e.g., a medication taken within exclusionary window at the time of first screening that would not be within exclusionary window at a later rescreen).

No subjects may be screened more than twice due to a screening failure result as defined above.

Subjects will be provided the results of abnormal clinical laboratory test values or abnormal clinical findings necessitating follow-up at the discretion of the participating site PI or appropriate sub-investigator. Research laboratory results will not be provided to the subject.

### **8.1.2 Screening Procedures for Leukapheresis**

For those subjects consented for leukapheresis, screening procedures, including screening laboratory evaluations, will be performed locally prior to the leukapheresis procedure. Refer to the protocol-specific MOP for details on the leukapheresis procedure.

### **8.1.3 Immunogenicity Evaluations**

#### Serological Immunogenicity Assays:

The following serological immunogenicity assays will be performed:

- IgG ELISA to the SARS-CoV-2 S (spike) protein.
- IgM and IgA ELISA to the SARS-CoV-2 S (spike) protein.
- Neutralization assay using a SARS-CoV-2 pseudovirus.
- Neutralization assay using a live wild-type SARS-CoV-2.

Preparation of blood samples and shipping instructions for serological immunogenicity assays are outlined in the protocol-specific MOP. Inability (e.g., loss of IV access) to collect all baseline samples on Day 1 will not exclude the subject from further participation in this study as long as a minimum of baseline serum for serological immunogenicity assays is collected.

#### Cellular Immunology Assays:

This trial will also investigate T cell immune responses using multiparametric flow cytometry.

Preparation of blood samples and shipping instructions for cellular immunology assays are outlined in the protocol-specific MOP.

The volume of venous blood to be collected for immunogenicity evaluations is presented in [Table 8](#).

### **8.1.4 Samples for Genetic/Genomic Analysis**

#### **8.1.4.1 Genetic/Genomic Analysis**

Stored PBMCs, including leukocyte samples obtained by leukapheresis, may be used in secondary research for sequencing of DNA from B cells to characterize B cell receptors and monoclonal antibodies. The DNA data may be used to synthesize antigen-specific antibodies to characterize antibody binding. Secondary research samples may also be used for other genomic analysis, including, but not limited to, single nucleotide polymorphisms (SNP) arrays, human leukocyte antigen (HLA) typing, transcriptomic analysis, evaluation of the immune response to the vaccine, and/or evaluation of any AE from the vaccine.

#### **8.1.4.2 Genetic Privacy and Confidentiality**

Any genetic data generated will be kept private. Informed consent permitting data sharing will be part of the consent process. Subjects will be informed that the evolution of genomic technology

and analytical methods raises the risk of re-identification, even when specimens are de-identified. No data that may identify specific subjects will be kept with the genetic data.

### 8.1.4.3 Management of Results

All genetic testing in this protocol will be performed for research only and is not performed in a Clinical Laboratory Improvement Amendments (CLIA) certified laboratory. Therefore, results will not be shared with the subjects.

## 8.2 Safety and Other Assessments

Study procedures are specified in the SOA. A study clinician, licensed to make medical diagnoses and listed on the Form FDA 1572 as the participating site PI or appropriate sub-investigator, will be responsible for all study-related medical decisions.

- Medical history:
  - A complete medical history will be obtained by interview of subjects at the screening visit. Subjects will be queried regarding a history of significant medical disorders of the head, ears, eyes, nose, throat, mouth, cardiovascular system, lungs, gastrointestinal tract, liver, pancreas, kidney, urologic system, nervous system, blood, lymph nodes, endocrine system, musculoskeletal system, skin, and genital/reproductive tract. A history of any allergies, cancer, immunodeficiency, psychiatric illness, substance abuse, and autoimmune disease will be solicited.
  - At all subsequent visits an interim medical history will be obtained by interview of subjects and any changes since the previous clinic visit or telephone call will be noted. The interim medical history should include an assessment for new medical conditions and symptoms suggestive of Protocol Specified AESIs, MAAEs and NOCMCs.
- Physical examination:
  - A full physical examination will be performed at the screening visit and a symptom-directed (targeted) physical examination will be performed if indicated at all other timepoints specified in the SOA.
    - A full physical examination will include assessments of the following organs and organ systems: skin, HEENT, neck, lungs, heart, liver, spleen, abdomen, extremities, lymph nodes (axillary and cervical), and nervous system.
    - Height and weight will be measured, and BMI calculated, at the screening visit only.
  - A symptom-directed (targeted) physical examination will be performed if indicated at all other timepoints specified in the SOA.
    - Targeted physical examinations should also include an assessment for signs suggestive of Protocol Specified AESIs, MAAEs and NOCMCs. Interim or unscheduled physical examinations will be performed at the

discretion of the participating site PI or appropriate sub-investigator, if necessary, to evaluate AEs or abnormal clinical laboratory test results.

- Reactogenicity assessments of solicited AEs occurring from the time of each vaccination through 7 days post each vaccination, will include an assessment of injection site reactions—erythema, edema/induration and pain, as well as systemic reactions—fever, fatigue, chills, myalgia (exclusive of the injection site), arthralgia, headache, and nausea. Pre-administration reactogenicity assessments will be performed immediately prior to each vaccination to establish baseline, then the vaccination will be given.
- Subjects will be observed in the clinic for at least 60 minutes post each vaccination. The vaccination site will be examined, post-administration reactogenicity assessments will be performed, and any AEs/SAEs will be recorded on the appropriate DCF prior to discharge from the clinic. The vaccination site will also be examined on Days 8 and 36.
- Vital signs: Vital sign measurements will include systolic and diastolic BP, HR, and oral temperature. Vital signs will be measured at timepoints specified in the SOA. On Days 1 and 29, vital sign measurements will be collected prior to vaccine administration. Vital signs assessed on Day 1 prior to the first vaccination will be considered as baseline. Subjects must not eat or drink anything hot or cold within 10 minutes prior to taking oral temperature.
- Clinical laboratory evaluations:
  - Fasting is not required before collection of clinical laboratory evaluations.
  - Serum pregnancy test will be performed locally by the site laboratory at the screening visit, and urine or serum pregnancy test will be performed locally by the site laboratory within 24 hours prior to each vaccination on Days 1 and 29, and as needed at interim or unscheduled visits for all women of childbearing potential. Results must be confirmed as negative prior to enrollment on Day 1 and administration of each vaccination.
  - Serology: hepatitis B surface antigen, hepatitis C virus antibody, and HIV types 1 and 2 antigen/antibody at the screening visit only.
  - Urine drug screen for drugs of abuse (components per the standard panel at the site laboratory) at the screening visit only.
  - Clinical screening laboratory evaluations (WBCs, Hgb, PLTs, ALT, AST, ALP, T. Bili, Cr, Lipase, PT, and PTT) will be collected at the screening visit.
    - Clinical screening laboratory evaluations will be performed locally by the site laboratory. The volume of venous blood to be collected for clinical screening laboratory evaluations is presented in Table 8.
  - Clinical safety laboratory evaluations (WBCs, Hgb, PLTs, ALT, AST, ALP, T. Bili, Cr, and Lipase) collected immediately prior to the first vaccination will serve as the baseline (Day 1), and will be repeated on Days 8, 29 and 36.

- Clinical safety laboratory evaluations will be performed locally by the site laboratory. The volume of venous blood to be collected for clinical safety laboratory evaluations is presented in Table 8. Inability (e.g., loss of IV access) to collect all baseline samples on Day 1 will not exclude the subject from further participation in this study as long as a minimum of baseline clinical safety laboratory evaluations is collected.
- Blood and urine will be collected at timepoints specified in the SOA.
- Memory aid:
  - All subjects will complete a Memory Aid from the time of each vaccination through 7 days post each vaccination (Days 1-8 for the first vaccination, and Days 29-36 for the second vaccination). Memory Aids will be reviewed with the subjects for any AEs (solicited injection site and systemic reactions, as well as unsolicited AEs), SAEs and concomitant medications during telephone calls on Days 2, 3, 30, and 31 and at clinic visits on Days 8 and 36.
- Telephone call:
  - Subjects will be contacted by telephone to query for safety events. AEs that have occurred since the previous clinic visit or telephone call will be solicited. Based on the information collected, subjects may be asked to return to the clinic for evaluation.
- Leukapheresis (only for those subjects consented for leukapheresis):
  - To support development of diagnostics, therapeutics and vaccines, a subset of subjects enrolled in cohorts 2, 3, 5, 10, and 11 may undergo leukapheresis to collect additional samples for secondary research. If enrollment in cohort 6 proceeds, a subset of subjects in this cohort may also undergo leukapheresis.
  - Leukapheresis is an outpatient procedure during which leukocytes will be selectively harvested; red cells and other blood components will be returned to the subject. In a typical leukapheresis procedure, approximately  $1-3 \times 10^9$  cells can be isolated with only minimal loss of red blood cells. No sedation is required. The procedure will be done by trained site staff and will be done using devices and procedures that conform to standard guidelines and SOPs.
  - For those subjects consented for leukapheresis, screening procedures, including screening laboratory evaluations, will be performed locally prior to the leukapheresis procedure.
  - Refer to the protocol-specific MOP for details on the leukapheresis procedure.

**Table 8: Venipuncture Volumes**

	Screening Visit 00, Day -42 to -1	Enrollment/Baseline Visit 01, Day 1	Visit 02, Day 2 1 day post Dose 1	Visit 03, Day 3 2 days post Dose 1	Visit 04 Day 8 +/- 1 day	Visit 05 Day 15 +/- 2 days	Visit 06 Day 29 +/- 2 days	Visit 07, Day 30 1 day post Dose 2	Visit 08, Day 31 2 days post Dose 2	Visit 09  Day 36 +/- 1 day	Visit 10  Day 43 +/- 2 days	Visit 11  Day 57 +/- 2 days	Visit 11A  Day 71 -7/+ 21 days	Visit 12  Day 119 +/- 7 days	Visit 13  Day 209 +/- 7 days	Final Study Visit 14  Day 394 +/- 14 days	Early Termination Visit	Total Volume of Blood Drawn (mL)	
Procedures		X					X												
Vaccination		X					X												
Clinical Laboratory Evaluations 	28	8			8		8			8								60	
Serum for Serological Immunogenicity Assays 		16				16	16			16	16	16		16	16	16	16	16 	144
PBMCs for Cellular Immunology Assays		80				40	16			16	40	16		40	40			16  or 40 	288
Serum for Secondary Research		16				8	8			8	8	8		8	8	8	8	8 	80
Serum for Product Assay Development		16				8	8			8	8	8		8	8	8	8	8 	80
Leukocytes for Secondary Research (subset of subjects)													62 						
Per Visit Blood Volume Total (mL)	28	136			8	72	56			56	72	48		72	72	32	-	652	
Cumulative Blood Volume (mL) (prior 56 days)		164			172	244	300			356	428	312		72	72	32			
Running Blood Volume Total (mL)	28	164			172	244	300			356	428	476		548	620	652	-		

 Inability (e.g., loss of IV access) to collect all baseline samples on Day 1 will not exclude the subject from further participation in this study as long as a minimum of baseline clinical safety laboratory evaluations and serum for serological immunogenicity assays are collected.

 These blood volumes are not included in the blood volume totals. Blood volume depends upon day of early termination visit.

 Only for those subjects consented for leukapheresis. These blood volumes are not included in the blood volume totals.

 Visits 09-14 windows should be based off the actual Visit 06 date.

 Subjects who participate in the optional third mRNA-1273 vaccination substudy will exit the Schedule of Activities for the main study between Visit 13 and the close of the window for Visit 14 and will not have Visit 14, instead will have Visit 14A and subsequent substudy visits. See [Section 12](#), [Appendix A](#) for the Schedule of Activities for the optional third mRNA-1273 vaccination substudy.

### **8.2.1 Procedures to be Followed in the Event of Abnormal Clinical Laboratory Test Values or Abnormal Clinical Findings**

If a physiologic parameter, e.g., vital signs, or clinical laboratory value, is outside of the protocol-specified range, then the measurement may be repeated once if, in the judgment of the participating site PI or appropriate sub-investigator, the abnormality is the result of an acute, short-term, rapidly reversible condition (e.g., stress, anxiety or “white coat syndrome”) or other source of error. A physiologic parameter may also be repeated if there is a technical problem with the measurement caused by malfunctioning, or an inappropriate measuring device (i.e., inappropriate-sized BP cuff).

All abnormal clinical findings or abnormal clinical laboratory tests values that occur post vaccination will be considered AEs.

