## **8.3 Adverse Events and Serious Adverse Events**

### **8.3.1 Definition of Adverse Event (AE)**

AE means any untoward medical occurrence associated with the use of an intervention in humans, whether or not considered intervention-related (21 CFR 312.32 (a)). An AE can therefore be any unfavorable and unintended sign (including an abnormal clinical laboratory finding), symptom or disease temporally associated with the use of medicinal (investigational) product.

Any medical condition that is present at the time that the subject is screened will be considered as baseline and not reported as an AE. However, if the severity of any pre-existing medical condition increases, it should be recorded as an AE.

AEs can be further divided into solicited AEs and unsolicited AEs. Solicited AEs are those for which the study team will specifically query the subject whether they occurred. Unsolicited AEs are those events that the subject report occurring without being queried about the specific event.

All AEs will be assessed for severity and relationship to study intervention ([Section 8.3.3](#)). Reporting of all AEs, solicited and unsolicited, will occur during the period from study product administration on Day 1 through 28 days after the second vaccination. After Day 57 through the end of study on Day 394, only SAEs, Protocol Specified AESIs, MAAEs, and NOCMCs will be reported as AEs.

All AEs, solicited and unsolicited, will be captured on the appropriate DCF. Information to be collected for AEs includes event description, date of onset, assessment of severity, relationship to study product and alternate etiology (assessed only by those with the training and authority to make a diagnosis and listed on the Form FDA 1572 as the participating site PI or appropriate sub-investigator), date of resolution, seriousness, and outcome. AEs occurring during the study-collection and reporting period will be documented appropriately regardless of relationship.

AEs will be followed to resolution or stabilization.

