3.2. Study Definitions and Derived Variables

The baseline value will be defined as the last value obtained prior to the first vaccination of study product. Treatment Group and Cohort will be used interchangeably.

The Williams mean is a variation of the geometric mean using $\log(1+x)$ transformation of the data, where x is each data point. The Williams mean is used in cases where 0 is a possible and/or reported value of the data.

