	100 µg (56-70 years)										
	25 µg (≥71 years)										
	50 µg (≥71 years)										
	100 µg (≥71 years)										

				None		Mild/ Grade 1		Moderate/ Grade 2		Severe/ Grade 3	
Timepoint	Treatment Group	N	N*	n	%	n	%	n	%	n	%
	All Subjects										

Note: The “Max Severity Post Baseline” rows indicate the maximum severity experienced by each subject at any time point post baseline, including unscheduled assessments.
N = Number of subjects enrolled and vaccinated; N* = Number of subjects that completed the visit.

Tables with Similar Format:

- Table 260: Laboratory Results by Parameter, Maximum Severity, Time Point, and Treatment Group – Alanine Aminotransferase***
- Table 261: Laboratory Results by Parameter, Maximum Severity, Time Point, and Treatment Group – Aspartate Aminotransferase***
- Table 262: Laboratory Results by Parameter, Maximum Severity, Time Point, and Treatment Group – Alkaline Phosphatase***
- Table 263: Laboratory Results by Parameter, Maximum Severity, Time Point, and Treatment Group – Total Bilirubin***
- Table 264: Laboratory Results by Parameter, Maximum Severity, Time Point, and Treatment Group – Serum Creatinine***
- Table 265: Laboratory Results by Parameter, Maximum Severity, Time Point, and Treatment Group – Serum Lipase***
- Table 266: Abnormal Laboratory Results Related to Study Treatment by Parameter, Maximum Severity, Time Point, and Treatment Group – Any Chemistry Parameter***
- Table 267: Abnormal Laboratory Results Related to Study Treatment by Parameter, Maximum Severity, Time Point, and Treatment Group – Alanine Aminotransferase***
- Table 268: Abnormal Laboratory Results Related to Study Treatment by Parameter, Maximum Severity, Time Point, and Treatment Group – Aspartate Aminotransferase***
- Table 269: Abnormal Laboratory Results Related to Study Treatment by Parameter, Maximum Severity, Time Point, and Treatment Group – Alkaline Phosphatase***
- Table 270: Abnormal Laboratory Results Related to Study Treatment by Parameter, Maximum Severity, Time Point, and Treatment Group – Total Bilirubin***

Table 271: Abnormal Laboratory Results Related to Study Treatment by Parameter, Maximum Severity, Time Point, and Treatment Group – Serum Creatinine*

Table 272: Abnormal Laboratory Results Related to Study Treatment by Parameter, Maximum Severity, Time Point, and Treatment Group – Serum Lipase*

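### The AE rule is not tied to the pre-dose Day 1 baseline, so an abnormality that predates vaccination and persists unchanged can be recorded as a post-vaccination AE

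*Protocol*

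**What the plan says.** Two sections of the protocol decide what becomes an AE.

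- Section 8.2.1: "All abnormal clinical findings or abnormal clinical laboratory tests values that occur post vaccination will be considered AEs".
- Section 8.3.1: "Any medical condition that is present at the time that the subject is screened will be considered as baseline and not reported as an AE". It adds that "if the severity of any pre-existing medical condition increases, it should be recorded as an AE". AE reporting "will occur during the period from study product administration on Day 1 through 28 days after the second vaccination".

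Other sections set a different reference point. Protocol 8.2 takes the sample drawn just before the first dose as baseline for the safety laboratory tests, and the Day 1 pre-dose reading as baseline for vital signs. SAP 3.2 agrees: "The baseline value will be defined as the last value obtained prior to the first vaccination of study product".

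On display, SAP Tables 138 to 140 have a row for any laboratory AE and a row for any vital-sign AE. Neither row has a definition. In the laboratory severity tables, the maximum-severity "rows indicate the maximum severity experienced by each subject at any time point post baseline, including unscheduled assessments". The vital-sign tables carry the same kind of row. SAP 9.3 puts every reported AE into the summaries and analyses.

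**The concern.** The reference point for deciding what is an AE (screening) is not the reference point for describing change after vaccination (Day 1 pre-dose). Up to 42 days can separate them. An abnormality that arises in that interval predates the vaccine, yet the wording does not keep it out of the post-vaccination AE count.

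Frequency and grade of unsolicited AEs is a primary endpoint (Protocol 3). The trial has no placebo arm (Protocol 4.2), so no control rate is available against which to offset such events. Cohorts have 10 or 15 subjects, so one or two such subjects would visibly move a cohort's percentage.

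**Working it through.** **Tracing one case through the text.** A subject has normal laboratory results at screening, a mildly abnormal value in the Day 1 pre-dose sample, and the same value on Day 8.

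1. *Entry.* Protocol 5.1, criterion 14 requires acceptable screening laboratory values, so a Day 1 abnormality is normally new since screening.
2. *Dosing.* The Schedule of Activities and Protocol 8.2 require only the pregnancy result to be confirmed before vaccination. The other Day 1 results need not be known.
3. *Exemption.* The abnormality was absent at screening, so 8.3.1 does not exempt it.
4. *Day 1 result.* It precedes product administration, so it falls outside the AE reporting period and is not itself an AE.
5. *Day 8 result.* It is an abnormal value obtained after vaccination, and the literal text of 8.2.1 makes it an AE.
6. *Later correction.* The Day 1 baseline in Protocol 8.2 and SAP 3.2 governs how values are analysed. No section uses it to remove a recorded AE.

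The same steps apply to a vital sign or clinical finding that starts between screening and the Day 1 assessment.

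**Size.** The plan gives no figure to reproduce and no prevalence of Day 1 abnormality. The following is an illustration for laboratory values only.

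- Analytes: 9 (WBC, hemoglobin, platelets, ALT, AST, ALP, total bilirubin, creatinine, lipase; Protocol 8.2).
- Subjects: 120 enrolled (Protocol 12.2).
- Assumed: *q*, the chance that an analyte is abnormal pre-dose on Day 1, from 0.5% to 5%.
- Assumed: *r*, the fraction of these still abnormal after dosing, from 25% to 75%.
- Assumed: independent analytes.

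Probability that a subject has at least one such AE: P = 1 − (1 − *qr*)^9. Expected number of subjects: 120 × P.

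| *q* | *r* = 25% | *r* = 50% | *r* = 75% |
|---|---|---|---|
| 0.5% | 1.1% (1.3) | 2.2% (2.7) | 3.3% (4.0) |
| 1% | 2.2% (2.7) | 4.4% (5.3) | 6.6% (7.9) |
| 2.5% | 5.5% (6.6) | 10.7% (12.8) | 15.7% (18.8) |
| 5% | 10.7% (12.8) | 20.4% (24.5) | 29.1% (34.9) |

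Lowest corner: 1 − (1 − 0.005 × 0.25)^9 = 1.1%. Highest corner: 1 − (1 − 0.05 × 0.75)^9 = 29.1%.

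The chance of at least one affected subject in a cohort of 15, 1 − (1 − P)^15, runs from 15.5% to 99.4%. In a cohort of 10 it runs from 10.6% to 96.8%.

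Positive correlation between analytes would lower these figures. Vital signs and clinical findings are not included and would add to them.

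**The case against.** The best defence is that 8.2.1 speaks of abnormalities that occur after vaccination, which can be read as new onset. AE reporting starts at product administration and onset dates are recorded, so a site could reasonably leave out an unchanged pre-dose abnormality. This reading is possible, but the protocol does not state it. Section 7.1.4, on subjects who discontinue study product, does limit AE reporting to new findings; 8.2.1 does not. Two sites could apply 8.2.1 differently.

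The SAP also gives a reader ways to see pre-existing abnormalities: Day 1 rows in the laboratory and vital-sign severity tables, laboratory change from baseline (Tables 290 to 298), laboratory shift tables (281 to 289), a listing of abnormal results with relatedness (Table 258), and separate tables of related laboratory abnormalities. These help interpretation but do not alter the AE counts. Relatedness filters only in part, because Protocol 8.3.4.2 lets a temporal relationship alone support a related classification.

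Several stronger readings are tempting, and the documents do not support them.

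- *That baseline is fixed at screening throughout.* The screening sentence concerns medical conditions. Laboratory values and vital signs have a Day 1 baseline.
- *That such abnormalities are certainly counted.* Only those still present after dosing could be, and only on the literal reading.
- *That the laboratory row of Table 138 takes the worst post-baseline grade.* It is undefined.
- *That 4% to 20% of subjects are affected.* 1 − (1 − *q*)^9 gives 4.4%, 8.6% and 20.4% for *q* = 0.5%, 1% and 2.5%, but this counts assumed pre-dose carriers before any allowance for persistence.
- *That the systolic entry limit of 150 mm Hg shows the same problem.* A level present at screening is already baseline under 8.3.1 if it counts as a condition, and a worsening rule applies.
- *That the halting rules are seriously exposed.* Criterion 5 of 7.1.1 needs three or more subjects with a related Grade 3 event in the same Preferred Term. The corresponding sentinel rule needs two. An unchanged pre-dose abnormality is an unlikely contributor.

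**Conclusion.** The gap is real. Taken literally, 8.2.1 and 8.3.1 allow an abnormality that arose after screening but before vaccination, and then persisted unchanged, to be recorded as a post-vaccination AE. No other section removes it. The bias is upward, in a primary endpoint without a control arm.

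Its size cannot be known from the documents. The range of about 1% to 29% of subjects rests wholly on the assumed prevalence, persistence and independence, and its width shows how little the documents settle. The point concerns the AE rule and the undefined AE rows. It does not show that the laboratory or vital-sign analyses use the wrong baseline.

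**What to change.** 1. **Protocol 8.3.1:** replace the reference to screening with a reference to the period before the first vaccination, ending with the Day 1 pre-dose assessment.
2. **Protocol 8.2.1:** state that a post-vaccination abnormality is an AE if it is new or of higher grade than the Day 1 pre-dose value, including one that recurs after returning to normal. Without the recurrence clause, a Grade 1 value that normalised by Day 8 and came back at Grade 1 on Day 36, after the second dose, would be lost.
3. **SAP Tables 138 to 140:** define the laboratory and vital-sign AE rows by the same rule.
4. **SAP displays:** keep the all-abnormality listings and the maximum-severity rows as they are, labelled as not adjusted for baseline.

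The cost is one sentence in each protocol section and one derivation rule in the SAP. The Day 1 values are already collected and listed (Listings 13 to 15), so no new data are needed. The downside is a somewhat lower reported AE count, with unchanged pre-dose abnormalities then appearing only in the laboratory and vital-sign tables and listings.
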